### 2.4 Safety Endpoint(s)

There are no specified safety endpoints. See section 8.2 for the methods to analyse safety data.

## 3 HYPOTHESIS AND DECISION RULES

For the non-inferiority test of CNC word score, the 95% CI (alpha=0.025 one-sided) for the mean paired difference (Kanso 2 NF versus Kanso 2 (no notch filters or standard omni) for the primary endpoint, Kanso 2 (no notch filters or standard omni) + ForwardFocus (standard omni) versus Kanso 2 (no notch filters and standard omni) and Kanso 2 (no notch filters or standard omni) versus Nucleus

8, respectively for the secondary endpoints) will be estimated. If the lower limit of the 95% CI of the mean paired difference is above -10%, the 'experimental SP' (Kanso 2 NF, Kanso 2 [no notch filters] + ForwardFocus [standard omni], and Kanso 2 [no notch filters or standard omni], respectively for the primary and secondary endpoints) is regarded as non-inferior to the 'control SP' on that measure.

## **3.1 Statistical Hypothesis**

### **3.1.1 Pass/Fail Criteria**

See hypotheses.

### **3.1.2 Primary Hypothesis**

Endpoint: Paired difference in percentage CNC Words correct in quiet (50 dB) with the Kanso 2 (notch filters) and Kanso 2 (no notch filters) Sound Processors; higher score corresponds with a better outcome.

H0: Words in quiet (50 dB CNC words) scores (% words correct) with the Kanso 2 NF Sound Processor (treatment) are inferior to those with the Kanso 2 Sound Processor (control)

$$\text{Kanso 2 NF} - \text{Kanso 2} \leq -10\%$$

H1: Words in quiet (50 dB CNC words) scores (% words correct) with the Kanso 2 NF Sound Processor (treatment) are non-inferior to those with the Kanso 2 Sound Processor SNR-NR on (control)

$$\text{Kanso 2 NF} - \text{Kanso 2} > -10\%$$

### **3.1.3 Secondary Hypotheses**

Endpoint: Paired difference in percentage CNC Words correct in quiet (50 dB) with the Kanso 2 + FF (standard omni) and Kanso 2 (standard omni) Sound Processors

H0: Words in quiet (50 dB CNC words) scores (% words correct) with the Kanso 2 FF Sound Processor (standard omni) (treatment) are inferior to those with the Kanso 2 Sound Processor (standard omni) (control)

$$\text{Kanso 2 FF} - \text{Kanso 2} \leq -10\%$$

H1: Words in quiet (50 dB CNC words) scores (% words correct) with the Kanso 2 FF Sound Processor (treatment) are non-inferior to those with the Kanso 2 Sound Processor (standard omni) (control)

$$\text{Kanso 2 FF} - \text{Kanso 2} > -10\%$$

Endpoint: Paired difference in percentage CNC Words correct in quiet (50 dB) with the Kanso 2 and Nucleus 8 Sound Processors

H0: Words in quiet (50 dB CNC words) scores (% words correct) with the Kanso 2 sound processor (treatment) are inferior to those with the Nucleus 8 Sound Processor (control)

$$\text{Kanso 2} - \text{Nucleus 8} \leq -10\%$$

H1: Words in quiet (50 dB CNC words) scores (% words correct) with the Kanso 2 sound processor (treatment) are non-inferior to those with the Nucleus 8 Sound Processor SNR-NR on (control)

$$\text{Kanso 2} - \text{Nucleus 8} > -10\%$$

---

## **3.2 Statistical Decision Rules**

No adjustments will be made for multiplicity of testing. All p-values reported will be at the nominal 5% significance level.

## **4 INTERIM ANALYSES, UNBLINDING AND INDEPENDENT DATA MONITORING COMMITTEE REVIEW**

### **4.1 Interim Analyses and Unblinding**

Not applicable

### **4.2 Independent Data Monitoring Committee Review**

Not applicable

## **5 ANALYSIS POPULATIONS**

This study has a non-inferiority design; therefore, the primary analysis will be based on the PP population. If non-inferiority is demonstrated, the test of superiority in the Per Protocol (PP) and the Intent-To-Treat (ITT) analysis sets will follow.

For cases in which the ITT and PP populations lead to the same conclusions and final interpretations about the treatment effect, the results will be considered to not be influenced by underlying factors such as missing data and protocol deviations, and the results would be considered to be robust and consistent under different analysis populations. A statement to reflect this will be included in the CIR.

For cases in which the ITT and PP populations lead to different final interpretations or conclusions, the results will be reported for both analysis sets and the differences in outcomes will be identified and explored.

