9.5 Analysis Populations

The analysis of the primary endpoint will be based on the Intent-To-Treat (ITT) and Per Protocol (PP) analysis populations in order to support a conclusion of non-inferiority. The inclusion of both ITT and PP populations has been chosen to assess the robustness of the study results and the consistency of the study measures under different analysis populations.

This study has a non-inferiority design; therefore, the primary analysis will be based on the PP population.

For cases in which the ITT and PP populations lead to the same conclusions and final interpretations about the treatment effect, the results will be considered to not be influenced by underlying factors such as missing data and protocol deviations, and the results would be considered to be robust and consistent under different analysis populations. A statement to reflect this will be included in the CIR.

For cases in which the ITT and PP populations lead to different final interpretations or conclusions, all of the results will be reported and the differences in outcomes will be identified and explored.

Intent-to-Treat Population

The Intent-to-Treat Population will include all subjects who receive the treatments and have at least one set of paired treatment and control measurements from any endpoint, regardless of protocol deviations and missing data.

Per Protocol Population

The Per Protocol Population will include all subjects who receive the treatments and have at least one paired measurement from treatment and control, without major protocol deviations. Major deviations will be defined at the clean file meeting before data base lock.

It is possible that a treatment has not been administered in the intended counterbalanced order of presentation.

It is also expected that the sequence and period effects are minimal in this study if any. This study is not a full cross-over design, so period and sequence effects will not be assessed, without the consequence to bias the study conclusion.

Safety Population

The Safety Population will include all treated subjects. The Safety Population will be used for the safety data analysis.

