13 DEVIATIONS FROM THE CLINICAL INVESTIGATION PLAN

The Investigator(s) must not deviate from the CIP, except in case of an emergency to protect the safety and well-being of the subject(s). Such deviations will be documented by the site personnel in the source documentation for the subject and reported to the relevant EC as per institutional requirements and to the Sponsor as soon as possible, but not later than 7 working days from the date of the emergency.

If there is a deviation from CIP-defined assessments or parts thereof are omitted or completed incorrectly, the deviation will also be documented by the site personnel in the source documentation for the subject. Depending on the type or severity of the deviation the Investigator may be required to notify the EC, particularly if the deviation potentially impacts subject safety, performance of IMD and/or comparator, or data integrity.

All CIP deviations will be documented in the eCRF to enable analysis and reporting by the Sponsor in the Clinical Investigation Report (CIR), or to the relevant regulatory authority(s), if applicable.

Gross misconduct on behalf of an Investigator, such as intentional non-compliance with CIP or GCP requirements or fraud, will result in disqualification of the Principal Investigator and/or Investigational Site from participation in the investigation. Data provided by the Principal Investigator or Investigational Site will be excluded from the per-protocol analysis group.

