### **5.1 Intent-to-Treat Analysis Set**

The Intent-to-Treat Population will include all subjects who receive the treatments and have at least one set of paired treatment and control measurements from any endpoint, regardless of protocol deviations and missing data.

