### **5.2 Per Protocol Analysis Set**

The Per Protocol Population will include all subjects who receive the treatments and have at least one paired measurement from treatment and control, without major protocol deviations. Major deviations will be defined at the clean file meeting before data base lock.

It is possible that a treatment has not been administered in the intended counterbalanced order of presentation.

It is also expected that the sequence and period effects are likely to be negligible in this study.

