### **5.6 Protocol Deviations**

Major protocol deviations will be listed for the safety population with the reason(s) for the deviation(s). Major deviations will include violations of eligibility criteria, incorrect order of administration of the SPs, or an incorrect administration of a test condition.

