### **6.2 Missing, Unused or Spurious Data**

Missing data will not be imputed.

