## **8 STATISTICAL ANALYSES**

### **8.1 Efficacy Analysis**

#### ***Primary and Secondary Speech Perception Endpoints:***

Words in quiet scores at different speech testing conditions will be listed and summarised descriptively by treatment group and study population. Figures as appropriate to further describe the data may be presented.

For the non-inferiority test of words in quiet scores, the 95% CI (alpha=0.025 one-sided) for the mean paired difference will be estimated. If the lower limit of the 95% CI of the mean paired difference is above -10%, the treatment condition is regarded as non-inferior to the control in term of words in quiet perception. The non-inferiority margin of -10% for words in quiet scores (monosyllables) is also based on clinical consensus.

While sequence and period effects are expected to be minimal in this single day, in booth study of approximately 3 hours duration, an analysis of variance (ANOVA) that considers the sequence and period effects will also be conducted as a supportive analysis to the paired t-test. The model will be formulated as follows:

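### Agreement between the ITT and PP sets cannot show that missing data had no influence, because a wholly missing score is absent from its comparison in both sets

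*SAP*

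**What the plan says.** CIP 9.5 introduces the rule with "For cases in which the ITT and PP populations lead to the same conclusions and final interpretations about the treatment effect", and SAP 5 repeats it. In that event "the results will be considered to not be influenced by underlying factors such as missing data and protocol deviations", the results count as robust across populations, and the CIR is to say so.

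The rest of the plan fixes who contributes to each comparison:

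- **ITT (SAP 5.1).** Subjects must receive the treatments and "have at least one set of paired treatment and control measurements from any endpoint", whatever their deviations or missing data.
- **PP (SAP 5.2).** Subjects need at least one treatment-control pair and no major deviation. "Major deviations will be defined at the clean file meeting before data base lock".
- **Major deviations (SAP 5.6).** "Major deviations will include violations of eligibility criteria, incorrect order of administration of the SPs, or an incorrect administration of a test condition". A missing score is not named.
- **Missing data (SAP 6.2).** "Missing data will not be imputed".
- **Test (SAP 8.1).** A comparison passes if the lower 95% confidence limit of the mean paired difference lies above -10 percentage points. A supportive ANOVA with device, period, sequence and subject accompanies it.
- **Withdrawals (CIP 7.2.6).** Participating subjects who withdraw are not replaced.

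**The concern.** The sentence fixes in advance a conclusion about missing data and rests it on a comparison of two analysis sets. That comparison is informative only if the sets treat missing scores differently. They differ by protocol deviations. A score that was never obtained is unavailable to both, so the two analyses could agree whatever that score would have been.

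What is at stake is one statement in the report. If scores were missing, readers could be told that this had no influence, on evidence that cannot bear on the question. No other planned analysis answers it: SAP 6.7 and 8.3 are marked not applicable, and the ANOVA is there for sequence and period effects and plays no part in the agreement rule.

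**Working it through.** **Step 1: the plan's own figure.** Inputs from CIP 9.4 and SAP 1.3: margin 10, SD of differences 7.5, two-sided alpha 0.05, power 0.90. The assumed true difference is not stated; I take 0. For a paired t test, power = 1 - F(t(0.975, n-1); n-1 df, noncentrality 10√n/7.5), where F is the noncentral t distribution function. This gives 0.896 at n = 8 and 0.937 at n = 9, so n = 9 is reproduced. Then 9/(1 - 0.25) = 12, the enrolment in CIP 7.2.3.

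**Step 2: who contributes a difference.** Take any one comparison, for example Kanso 2 NF minus Kanso 2.

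| Subject | In the ITT comparison? | In the PP comparison? |
|---|---|---|
| Both scores, no major deviation | yes | yes |
| Both scores, major deviation | yes | no |
| One score missing, another endpoint's pair observed | no difference exists | no difference exists |
| No pair at all | not in the set | not in the set |

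Only the second row separates the sets. In the third row the subject may belong to ITT through another endpoint, but belonging does not create a difference for this one. If the clean file meeting classed the omission as major, the subject would also leave PP for the other comparisons; the affected comparison would still be the same in both sets. With no subject in the second row, ITT and PP hold the same 11, 10 or 9 differences and agree with certainty.

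**Step 3: how bad missing values must be to reverse a pass.** Assumptions: 12 treated, j missing, n = 12 - j completers with mean m and SD 7.5, and all missing differences set to a common value x.

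- Combined mean: M = (n·m + j·x)/12
- Combined sum of squares: SS = (n - 1)·7.5² + (n·j/12)·(m - x)²
- Lower limit: M - 2.201·√(SS/11)/√12, where 2.201 = t(0.975, 11)
- Solve for x where the lower limit equals -10.

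Example, j = 3, m = -3. Completers alone: -3 - 2.306 × 7.5/√9 = -8.77, a pass. At x = -11.83: M = (-27 - 35.5)/12 = -5.21; SS = 450 + 2.25 × 8.83² = 625.6; √(625.6/11) = 7.54; lower limit = -5.21 - 2.201 × 7.54/3.464 = -10.0.

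| Missing of 12 | Completer mean needed to pass | Tipping value at m = 0 | Tipping value at m = -3 |
|---|---|---|---|
| 1 | above -5.0 | -31.6 (4.2 SD below m) | -20.4 (2.3 SD) |
| 2 | above -4.6 | -20.3 (2.7 SD) | -14.2 (1.5 SD) |
| 3 | above -4.2 | -15.7 (2.1 SD) | -11.8 (1.2 SD) |

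**Step 4: effect on error rates, as a bound only.** This was simulated with 12 treated and total SD 7.5, losing the 1, 2 or 3 subjects with the worst true decrement. Scoring noise of 6.1 to 7.0 points is assumed, from binomial-type variation over 100 words at 80% and 50% correct; these inputs are not in the documents. At a true mean of -10 the false-pass rate is 2.5% with no loss or random loss, and 3.7-4.9%, 4.9-7.6% or about 6-10% under this extreme selection. At a true difference of 0, a full-data fail becomes a pass in under 1% of trials.

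**The case against.** The strongest reply is that there may be nothing to miss. Testing is one supervised visit of up to 3 hours, a subject who hears poorly normally scores low rather than not at all, and CIP 7.3 allows retesting after a product fault. Missing scores would also be visible, because SAP 6.1 lists all data with counts of non-missing observations and SAP 7 gives reasons for discontinuation. All of this stands, and it limits the weight of the point. It does not make agreement informative about an absent score.

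Agreement can say something about partial or wrongly run tests. CIP 13 has them documented ("If there is a deviation from CIP-defined assessments or parts thereof are omitted or completed incorrectly"), and if they are then classed as major they do separate the sets. That is why the point is confined to wholly missing scores. The ANOVA may keep a subject's other device scores, but it does not observe the missing one.

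Three stronger readings are tempting, and the documents do not support them:

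- **That 3 of 12 treated subjects are expected to be lost.** The 25% in CIP 7.2.3 applies to enrolled subjects, whom CIP 7.2.5 defines as those who have signed consent. CIP 9.4 also assigns the extra subjects to higher than expected variability. Someone who leaves before trying a device cannot be lost because of it.
- **That loss will depend on outcome.** CIP 8.3 advises returning to one's own processor if intelligibility falls, which is a possible route. Nothing says it will be taken.
- **That the CIR will state in terms that missing data had no influence.** The plan calls for a statement reflecting the rule and does not fix its wording.

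**Conclusion.** The inference rule is wrong for wholly missing scores. This follows from the set definitions, the absence of imputation and the use of paired differences, and it needs no numerical assumption. The primary test, margin, sample size and decision rule are unaffected.

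The consequence is small and conditional, and it is nil if every treated subject has every score. One missing score would rarely matter. Two or three could matter if the completer mean were already unfavourable, at around -3. The tipping values rest on a completer SD of 7.5 and a common value for the missing differences. The simulated error rates rest further on deliberately extreme selection and assumed scoring noise, so they are a bound and not a forecast. The change is still worth making, because it corrects what the report may conclude and costs very little.

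**What to change.** 1. In SAP 5 and CIP 9.5, remove missing data from the agreement sentence, so that agreement between the sets supports robustness to protocol deviations only.
2. In SAP 8.1, add a conditional supportive analysis. If any treated subject lacks either score of a comparison that passed, combine all observed differences with one common value assigned to the missing ones. Report the value at which the lower limit reaches -10 points, beside the worst observed difference. Label it as an all-treated analysis, since a subject with no pair lies outside ITT.

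The first change cures the faulty inference. The second gives the report something valid to say if scores are in fact missing. The cost is a small SAP revision, a minor CIP amendment with ethics committee notification under CIP 18, and at most one short table. A pass may look slightly less secure.

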### **5.1 Intent-to-Treat Analysis Set**

The Intent-to-Treat Population will include all subjects who receive the treatments and have at least one set of paired treatment and control measurements from any endpoint, regardless of protocol deviations and missing data.

### **5.2 Per Protocol Analysis Set**

The Per Protocol Population will include all subjects who receive the treatments and have at least one paired measurement from treatment and control, without major protocol deviations. Major deviations will be defined at the clean file meeting before data base lock.

It is possible that a treatment has not been administered in the intended counterbalanced order of presentation.

It is also expected that the sequence and period effects are likely to be negligible in this study.

### **5.3 Safety Analysis Set**

The Safety Population will include all treated subjects. The Safety Population will be used for the safety data analysis.

### **5.4 Other Analysis Sets**

Not applicable

### **5.5 Misallocations to Treatment**

Not applicable

### **5.6 Protocol Deviations**

Major protocol deviations will be listed for the safety population with the reason(s) for the deviation(s). Major deviations will include violations of eligibility criteria, incorrect order of administration of the SPs, or an incorrect administration of a test condition.

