7.2.3 Number of Subjects Required

The total number of subjects to be enrolled in the study to meet sample size calculation requirements is 12, which includes 3 additional subjects to account for an expected dropout rate of 25%.

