## **1.3 Sample Size Justification**

This study is a non-inferiority design, and sample size calculation was based on non-inferiority tests for CNC word scores. The sample size using a confidence interval method (two-tailed 95% confidence interval) was estimated to have a reasonable power to detect non-inferiority word scores for the listed hypotheses.

To reject the null hypothesis of inferior word perception in quiet for the new processor:

- A margin of non-inferiority of 10% has been chosen. That is, a true mean difference of up to 10% (defined as new-old) is acceptable and not considered a clinically meaningful change. This margin is based on clinical consensus, and previous feedback from the FDA.

- An expected standard deviation of difference scores of 7.5% for CNC words (50 dB), based on previous OTE studies investigating words in quiet.
- A significance level  $\alpha = 0.05$  (two-tailed).
- A desired power of 0.9.

Based on these assumptions, a sample size of 9 subjects is required to reject the null hypothesis. An increased sample size of 12 subjects will be enrolled, which will allow for the possibility that the variability in difference scores will be greater than expected and to account for the possibility of subject attrition.

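### The primary Per Protocol set drops a whole subject for errors outside the comparison, so valid Kanso 2 NF versus Kanso 2 pairs can be lost; the power cost is conditional

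*SAP*

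**What the plan says.** SAP section 5 makes PP the primary set because the design is non-inferiority. SAP 5.2 admits subjects who receive the treatments and "have at least one paired measurement from treatment and control, without major protocol deviations". Protocol 9.5 uses the same definition. Membership belongs to the subject, not to a particular comparison.

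SAP 5.6 then says what counts as major: "Major deviations will include violations of eligibility criteria, incorrect order of administration of the SPs, or an incorrect administration of a test condition". SAP 5.2 and protocol 9.5 leave the definition of major deviations to the clean file meeting before database lock.

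On order, SAP 5.2 concedes: "It is possible that a treatment has not been administered in the intended counterbalanced order of presentation". It adds that sequence and period effects are likely negligible, and protocol 9.5 also expects them to be minimal.

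Each subject is tested with four processors in one of four orders (Table 3 in protocol 7.2.7 and SAP 1.4). The primary contrast uses two of them, Kanso 2 NF and Kanso 2.

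On numbers, 9 subjects are required and 12 enrolled. Protocol 7.2.3 describes the 12 as a total "which includes 3 additional subjects to account for an expected dropout rate of 25" percent. Protocol 9.4 and SAP 1.3 give the increase two purposes: larger variability than expected, and attrition. Protocol 7.2.6 rules out replacing withdrawn participants.

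**The concern.** The primary endpoint is one within-subject difference. Whether it is valid depends on whether the Kanso 2 NF and Kanso 2 runs were done properly. A wrong setting in the Nucleus 8 or FF run says nothing about that, yet under SAP 5.2 with 5.6 it takes the subject out of the primary analysis.

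Order errors raise a similar question. In every row of Table 3, swapping Nucleus 8 and FF leaves Kanso 2 and Kanso 2 NF in their planned positions, but the swap is still an incorrect order and so a major deviation. This fits poorly with the SAP's own expectation that order effects are negligible.

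Such departures are foreseeable. Counterbalancing is promised only where possible (protocol 7.1.1, SAP Design Rationale). The adaptive procedure in protocol 7.3 can require retesting after a product change, and the documents do not say whether a retest counts as incorrect order.

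With 9 to 12 subjects, each lost pair is a visible share of the data. At stake is the precision of the primary comparison, and with enough losses its power.

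**Working it through.** **Inputs from the plan**
- Test: SAP 8.1 says "the 95% CI (alpha=0.025 one-sided) for the mean paired difference will be estimated"; non-inferiority is concluded if the lower limit is above -10%.
- Margin: "A margin of non-inferiority of 10% has been chosen" (SAP 1.3).
- SD: "An expected standard deviation of difference scores of 7.5% for CNC words (50 dB), based on previous OTE studies investigating words in quiet" (SAP 1.3).
- Target: "A desired power of 0.9" (SAP 1.3).

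**Assumption.** The plan states no true mean difference. I take 0 and vary it below.

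**Formula.** Paired t-test with n pairs: power = 1 - F(t(0.975, n-1)), where F is the noncentral t distribution with n-1 degrees of freedom and noncentrality 10 x sqrt(n) / 7.5.

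**Reproducing the plan's 9 and 12**
- n = 9: noncentrality 10 x 3 / 7.5 = 4.00, critical value 2.306, power 93.7%.
- n = 8: noncentrality 10 x 2.828 / 7.5 = 3.77, critical value 2.365, power 89.6%.
- So 9 is the smallest n reaching 0.9, as stated. The normal approximation, (7.5 x (1.960 + 1.282) / 10)^2 = 5.9, would give only 6, so the plan's figure matches the t-based calculation.
- 9 / (1 - 0.25) = 12, as stated.

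**Power by pairs left in the primary PP analysis**

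| Pairs | Lost from 12 | Power |
|---|---|---|
| 12 | 0 | 98.7% |
| 11 | 1 | 97.8% |
| 10 | 2 | 96.2% |
| 9 | 3 | 93.7% |
| 8 | 4 | 89.6% |
| 7 | 5 | 83.4% |
| 6 | 6 | 74.3% |

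Three losses for any reason are absorbed. The fourth leaves power 0.4 points below target; the fifth leaves a material gap.

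**Subject rule against contrast rule.** The documents give no deviation rate, so these rates are assumptions. If each condition is wrongly administered with probability e, the subject rule removes 1 - (1-e)^4 of subjects and the contrast rule 1 - (1-e)^2. At e = 5% these are 18.5% and 9.75%. Adding order errors in 10% of subjects raises the subject rule to 1 - 0.9 x 0.95^4 = 26.7%. The contrast rule stays at 9.75% if none of those order errors costs a primary pair, which is its best case. Average power over the binomial number retained:

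| Assumed errors | From 12: subject / contrast | From 9: subject / contrast |
|---|---|---|
| 3% per condition | 96.7% / 97.9% | 88.4% / 91.2% |
| 5% per condition | 94.6% / 97.1% | 83.9% / 89.3% |
| 5% per condition, 10% order | 90.9% / 97.1% | 77.3% / 89.3% |

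From 12 enrolled, power stays above 90% in every row. It falls below only when the full 25% dropout has happened first.

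**Sensitivity.** The spare subjects are also meant to cover a larger SD. With SD 9, power is 93.8% at 12 pairs, 91.2% at 11, 87.7% at 10 and 83.0% at 9, so one loss can be absorbed rather than three. With a true difference of -2 (SD 7.5), it is 91.9% at 12, 88.9% at 11 and 80.0% at 9.

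**The case against.** Several points on the other side stand.

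- A reader might infer that the rule forfeits the stated 90% power. The documents do not support that. Their own inputs give 93.7% at 9, enrolment of 12 absorbs three losses, and nothing shows that a fourth is likely in a single-visit study of about three hours at one site run by qualified audiologists.
- A reader might also infer that no order error can matter and that all should stay in PP. That goes too far. The main analysis is an unadjusted paired t-test, and the ANOVA with period and sequence is only supportive (SAP 8.1). Counterbalancing is therefore the main test's only protection against order effects. Kanso 2 precedes Kanso 2 NF in two rows of Table 3 and follows it in two, and an error that reverses them disturbs that balance. Negligible order effects are an expectation, not a finding.
- SAP 5.2 and 5.6 do not flatly contradict each other. One says order errors may occur; the other classes them. A strict PP set is a legitimate choice.
- Fewer pairs widen the interval and make non-inferiority harder to show, so no inflation of false claims has been demonstrated.

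Two defences do not remove the point. The Intent-to-Treat (ITT) set keeps these pairs, but PP is primary, and differing results are only reported and explored. The clean file meeting might narrow the definition, but SAP 5.6 already says what major deviations will include, and investigators are unblinded, so the scope is better fixed in advance.

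**Conclusion.** The point holds as a defect in the scope of the exclusion. As written, PP membership is all-or-nothing per subject, and an error confined to Nucleus 8 or FF can remove a valid primary pair with no gain in freedom from bias. This follows from the text and needs no assumed rate.

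The effect on power is conditional. At SD 7.5 and a true difference of 0, a shortfall against 0.9 needs at least four of 12 subjects lost, dropout and exclusions combined; after the full planned dropout, one exclusion gives 89.6% and two give 83.4%. A larger SD or a negative true difference shrinks that allowance. How likely such losses are cannot be judged from the documents. This is an inexpensive improvement to the analysis-set definition; it does not show the study to be underpowered.

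**What to change.** In SAP 5.2 and 5.6 and protocol 9.5:

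1. Define PP by contrast. A subject leaves a contrast for an eligibility violation, or because one of that contrast's two conditions was incorrectly administered.
2. Do not exclude for an order error that leaves the relative order of those two conditions unchanged. For an error that reverses them, state before any scores are seen whether the pair stays; either choice can be defended.
3. Reconcile SAP 5.6 with SAP 5.2, both on the expectation that order effects are negligible and on whether major deviations are already listed or still to be defined at the clean file meeting. Say how a retest under the adaptive procedure is classed.
4. List all order errors, use the actual period in the supportive ANOVA, and report n for each contrast.
5. In SAP 1.3 and protocol 9.4, say that the three extra subjects must also cover PP exclusions.

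The cost is wording in two documents. The downside is that the PP n may differ between the three contrasts.
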